2. GENERAL ANALYSIS DEFINITIONS

As this is a virtual study, there are no planned in-person clinic visits for measuring key endpoints on the study participants. Data collection via smartphone, Fitbit device, and claims will continue throughout the 9-month duration of the study. While the focus of the first 12-week, double-blind treatment duration is to establish the primary and key secondary objectives related to primary and secondary effectiveness endpoints, the latter 6 months (i.e., Month 3 until Month 9) of the study (when no study intervention is provided) are aimed to explore multiple objectives by collecting additional follow-up data on PROs, daily activity, and HRUs and generate hypotheses of interest for future studies.

Unless stated otherwise, following the intent-to-treat (ITT) principle, analyses of the primary and secondary endpoints will be based on the full analysis set (FAS) and include data collected in the 12-week, double-blind treatment period. Where meaningful, these analyses may also be repeated using the per protocol analysis set. Analysis based on full analysis set (FAS) will also be extended to the full study data period (up to the end of the 9-month long study). In a similar way, exploratory endpoints will be analyzed according to the randomized intervention groups by using data from both the 12-week, double-blind treatment period and the 9-month study duration, respectively.

2.1. Time Windows

In this virtual study, the randomization date will refer to the day of randomization of an eligible participant. Once randomized, study intervention will be shipped and delivered to the randomized participant directly, and therefore, the first study intervention may be started by a participant a few days after the actual randomization date. This will be considered the date of starting study intervention, or, a reference day (Study Day 1). Scheduled study intervention will end after 12 weeks. After Week 12, participants will be followed up to Month 9 without receiving any further study intervention. Total study days will be numbered relative to the Study Day 1 for each participant up to the end of the 9-month long study. All measurements will be arranged in a chronological order relative to Study Day 1. Participants will be instructed and notified by the study app on their smartphone to confirm taking the study intervention on schedule and completing

all necessary patient reported outcome (PRO) measurements. Study app is programmed to allow PRO measurements to be recorded only within a pre-specified window of days around each scheduled time point.

The primary, secondary and exploratory variables (ie, KCCQ, and its individual domains, daily step count, daily floors climbed, PGIC and PGI-S, participant satisfaction survey, etc.) will be measured at specific time points as identified in the protocol, using either a smartphone-based mobile app or, the Fitbit device, as is relevant, registered by the study participant. Measurements taken closest to the planned (target) time points will be considered for the endpoint analyses and will be appropriately assigned to a time window to allow reasonable variations around the target day. Endpoint for analyses and summaries is the last recorded postbaseline data.

Daily activity measurements via the Fitbit device will be collected continuously from the time study started (ie, when both the smartphone and the Fitbit are linked by a participant). Fitbit daily activity data will be aggregated into averages over 2-week intervals starting with a baseline period (ie, Baseline = average of Study Day 1 to Study Day 14) and similarly over the entire post-baseline study duration for each participant. This is to allow capturing a robust length of physical activity for each participant using the Fitbit device and minimizing variability associated with measurements in shorter time spans. The end-of-treatment (EOT) average value of the step count will be the average of the last 14 days prior to the last dose of study intervention, regardless of when the last dose is taken.

Claims data will be extracted as access to participant-level information becomes available. This will include clinical outcomes (including hospitalizations for HF and/or other reasons) coded using International Statistical Classification of Diseases and Related Health Problems (ICD)-9 and ICD-10 as appropriate.

Time windows will not be applied to summarize the safety data collected through claims. Self-reported safety data will be summarized through Week 12 (Day 87).

Table 1 presents the time windows and the target days for each time of measurement defined in the protocol.

Table 1: Measurement Windows

Parameter	Time Interval (label on output)	Time Interval (Day)*	Target Time Point (Day)
KCCQ (and its individual domains); PGIC and PGI-S; participant satisfaction survey	Screening/Baseline	-21 to <1	1
	Week 2	11 to 17	14
	Week 4	25 to 31	28
	Week 6	39 to 45	42
	Week 12	81 to 87	84
	Month 6	161 to 175	168
	Month 9	245 to 259	252
Daily Step Count / Daily Floors Climbed **	Baseline to Week 2	1 to 14	
	Week 3 & Week 4	15 to 28	
	Week 5 & Week 6	29 to 42	
	Week 7 & Week 8	43 to 56	

Parameter	Time Interval (label on output)	Time Interval (Day)*	Target Time Point (Day)
	Week 9 & Week 10	57 to 70	
	Week 11 & Week 12	71 to 84	
	
	Week 35 & Week 36	238 to 252	

*Relative to Study Day 1

** Measurements over a 2-week interval with ≥ 100 daily steps to allow capture of physical activity

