- d. Includes up to 36 months of historical medical and pharmacy claims data for eligibility confirmation. This data collection will begin upon signing of the informed consent.
- e. Participant-reported adverse events to the call center occurs from the time of informed consent until 30 days after the end of treatment (ie, the last dose of study intervention). Adverse events from medical claims data occurs from the time of informed consent to the end of study.

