Due to the virtual method of data collection for this study, there will be 2 types of adverse event data collection, one by participants instructed to self-report any adverse events to a call center, and the other by an analysis of medical claims data from the participant's provider to their insurance system. Participant-reported adverse events to the call center will be captured from the time of informed consent until 30 days after the end of treatment (ie, the last dose of study intervention) and adverse events from medical claims data from the time of informed consent to the end of study.

After the treatment period plus 30 days, serious adverse events will be identified solely through medical claims data. Adverse events that occur during the treatment period plus 30 days identified from medical claims will be aggregated by treatment assignment when unblinding is available. In addition, for this time period, self-reported adverse events from the call center will be summarized in a listing. Serious adverse event data from medical claims for the 9-month study period will be aggregated by treatment assignment.

HYPOTHESIS

The primary hypothesis is that canagliflozin is superior to placebo as assessed by improvement in the TSS on the KCCQ scale during the 3-month, double-blind treatment period.

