Adverse events will be captured through medical claims (from the time of informed consent to the end of study) and by the call center (from the time of informed consent until 30 days after the end of treatment). After the treatment period plus 30 days, serious adverse events will be identified solely through medical claims data. Adverse events that occur during the treatment period plus 30 days identified from medical claims will be aggregated by treatment assignment when unblinding is available. In addition, for this time period, self-reported adverse events from the call center will be summarized in a listing. Serious adverse event data from medical claims for the 9-month study period will be aggregated by treatment assignment.

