Baseline for daily step count and daily floors climbed variables will be defined by averaging the daily values over a 14-day interval starting with the first dose date. These data will be organized into a vertical file format to read one record per participant for averages over each 2-week interval during the entire study (including the EOT/EOS values, as applicable).

Claims Data – AEs, HRUs, Clinical Outcomes

Claims data pertaining to AEs of interest (as defined in the protocol), number of prescription fills, HRUs, and clinical outcomes reported with appropriate ICD codes applied at the individual participant level will be organized with one record for each incident (ie, hospitalization, etc.) date. Adverse events of interest include all severe hypoglycemic events, acute kidney injury, fractures, diabetic ketoacidosis, and lower limb amputation.

In addition, the following adverse events will be examined: hypotension; Fournier’s gangrene; genital mycotic infections; urinary tract infections (including urosepsis and pyelonephritis); increased urination; and hypersensitivity reactions including angioedema and anaphylaxis.

Self-reported AE data – Data from participants self-reporting adverse events (AEs) to a Call Center (set up by Care Innovations) will be manually submitted directly to the Sponsor (i.e. Janssen Safety [GMS]) for appropriate evaluation and analysis. Janssen Safety (GMS) will extract participant-reported AEs and transfer data to PRA for upload into the CCDS. Self-reported events will be captured from the date of the first dose of study intervention through the end of treatment (Month 3) plus 30 days. A listing of these self-reported AE may be produced based on available data.

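### SAP 2.1 ends the self-reported safety summary at Day 87, but the protocol requires these events to be listed for the treatment period plus 30 days

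*SAP*

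**What the plan says.** **Protocol.** Section 3 sets the collection window: "Participant-reported adverse events to the call center will be captured from the time of informed consent until 30 days after the end of treatment". Footnote e of the Schedule of Activities (1.3) repeats it and equates end of treatment with the last dose. Section 8.3.1 gives the same window. It then describes how claims events in the treatment period plus 30 days will be aggregated, and continues: "In addition, for this time period, self-reported adverse events from the call center will be summarized in a listing". Section 3 carries the same sentence in the same context. The listing is therefore definite and its period is treatment plus 30 days.

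**SAP 2.1 (Time Windows).** "Self-reported safety data will be summarized through Week 12 (Day 87". The sentence directly before it exempts claims-based safety data from any time window.

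**SAP 5.1.2 (Data Handling Rules).** "Self-reported events will be captured from the date of the first dose of study intervention through the end of treatment (Month 3) plus 30 days". It then says: "A listing of these self-reported AE may be produced based on available data".

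**SAP 6 and 6.1.** The opening line of section 6 bases safety summaries on claims, whereas SAP 2.3.4 speaks of safety data from all sources. Section 6.1 asks for all call-center reports with no day limit and has them coded in MedDRA. It analyzes claims events through 30 days after last dose and over the 9 months. It lists events between consent and the day before first dose without naming the data source. It also states that call-center and claims data will not be reconciled.

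**The concern.** The SAP gives the same call-center data a capture window that runs to treatment plus 30 days and a summary window that stops about a month earlier. The protocol's reporting period matches the longer one. A programmer who applies SAP 2.1 literally would produce a self-report summary shorter than the one the protocol promises. Day 87 is the upper edge of the Week 12 questionnaire window in SAP Table 1, which has no evident bearing on safety follow-up.

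The claims analysis in SAP 6.1 uses diagnosis codes to pick out serious events and a named set of events of interest. A non-serious event outside that set can appear only through self-report. If the self-report display stops early, such events after treatment are not shown, and the two safety sources cover different periods.

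The start of the window also differs: first dose in SAP 5.1.2, informed consent in the protocol. This is a smaller matter of alignment.

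**Working it through.** **Inputs**
- Last day of treatment: target Day 84, window ±3 days, so Days 81 to 87 (Protocol 1.3; SAP Table 1).
- SAP summary cut-off: Day 87 (SAP 2.1).
- Required follow-up: 30 days after last dose (Protocol 3, 8.3.1 and Schedule of Activities footnote e).
- Pre-dose period: screening up to 28 days before Baseline, and Baseline up to 7 days before Day 1 (Protocol 1.3). The note in the same table labels Day -28 to 0 as screening.

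**Step 1. Reproduce the SAP's figure.** 84 + 3 = 87, the upper limit of the Week 12 window.

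**Step 2. Days omitted at the end.** With last dose on Day L, the protocol's reporting period ends on Day L + 30. Days omitted = max(0, L + 30 − 87) = max(0, L − 57).

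| Last dose (Day L) | Period ends (Day L + 30) | Days omitted | Share of the 30 days |
|---|---|---|---|
| 57 or earlier | 87 or earlier | 0 | 0% |
| 70 | 100 | 13 | 43% |
| 81 | 111 | 24 | 80% |
| 84 | 114 | 27 | 90% |
| 87 | 117 | 30 | 100% |

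For a last dose on Day 84 the omitted days are 88 to 114. As a share of treatment plus follow-up, that is 27/114 = 23.7%.

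**Step 3. The start of the window.** A first-dose start leaves the consent-to-Day-1 interval outside SAP 5.1.2. Its maximum is 28 + 7 = 35 days if the two column headings are added, or about 28 days if the note is taken as the whole pre-dose span. The lower bound is close to zero.

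**Step 4. Does other SAP text close the end gap?** SAP 5.1.2 keeps the 30 days in the capture window, so the data should be in the database. The request in SAP 6.1 for all call-center reports points the same way. Neither sentence changes the summary cut-off in SAP 2.1, and the only listing sentence in SAP 5.1.2 is permissive. Claims summaries cover the period, but for a restricted set of events and with no reconciliation to the self-reports.

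**The case against.** The strongest reply is that little is at risk. The protocol, not the SAP, governs what the call center collects. SAP 5.1.2 retains reports through the 30 days, and SAP 6.1 asks for every report without a cut-off and passes them into the study data package. SAP 6 makes claims the basis of the safety summaries, and those run to 30 days after last dose and beyond. SAP 2.1 limits a summary and does not mention a listing. The day count depends on when treatment stopped, and the documents give no expected number of self-reports, so the effect in events is unknown.

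Most of this stands, and it rules out three stronger readings that a reader might infer:

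- *Late reports are discarded.* The documents do not support this. They are collected and retained; what SAP 2.1 shortens is the summary.
- *The post-treatment month disappears from safety reporting.* It does not, because claims events in that month are summarized.
- *The protocol requires pre-dose self-reports in the listing.* Its capture window starts at consent, but in sections 3 and 8.3.1 the listing is tied to the treatment period plus 30 days. SAP 6.1 also lists pre-dose events, though without saying whether self-reports are among them. The start of the window is therefore a mismatch in capture wording, not a shown loss.

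One further point can be made for the SAP. In the opening text of protocol 8.3, the listing sentence follows a reference to the 3-month double-blind period, so read alone it could support a cut-off near Week 12. Sections 3 and 8.3.1 and the synopsis remove that ambiguity, because there the sentence follows the treatment period plus 30 days.

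The reply does not remove the direct conflict between SAP 2.1 and both the protocol and SAP 5.1.2. Nor does it make claims a substitute for self-reports, since reconciliation is expressly excluded.

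**Conclusion.** The SAP is wrong as written at the end of the window. It sets a cut-off for self-reported safety data that falls short of the protocol's reporting period and of its own capture period. The shortfall in the self-report summary is 27 of 30 post-treatment days for a last dose on Day 84, within a range of 24 to 30 days for participants who finish on schedule. Participants who stop by Day 57 are unaffected.

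These counts assume that SAP 2.1 is applied literally and that end of treatment means last dose, as the protocol defines it. They measure days of coverage, not events.

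The first-dose start in SAP 5.1.2 is a secondary inconsistency with the protocol. A plausible origin is that the SAP names protocol Amendment 1 as its basis, while the protocol's amendment history records the move from first dose to consent under Amendment 2. The conclusion does not depend on that explanation. No effectiveness endpoint is affected. The point should be corrected because, left alone, it would truncate safety reporting that the protocol requires or leave its extent to the programmer.

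**What to change.** - **SAP 2.1:** replace the Day 87 limit so that self-reported safety data are summarized through last dose plus 30 days.
- **SAP 5.1.2:** start the capture window at informed consent, and change the listing of self-reported events from optional to definite (*will be produced*).
- **SAP 6.1:** state that the listing of events between consent and first dose includes self-reported events.

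The cost is a few sentences of SAP text and the matching output specifications. The protocol already requires collection over the full window, so no new data, protocol amendment or change to the effectiveness analyses is needed.

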2.2. Pooling Algorithm for Analysis Centers

This is a virtual study with multiple IHNs competitively enrolling HF patients to meet the overall study enrollment target. Therefore, from the analytical perspective, no separate sites exist for pooling to be applicable. It will be considered a single center study.

2.3. Analysis Sets

An overview of the different analysis sets and their usage is presented in [Appendix 4: Usage of the Analysis Sets](#).

2.3.1. All Randomized Analysis Set

The all randomized analysis set includes all participants who are randomly assigned to a study treatment. In order to adhere to the ITT principle, analyses based on all randomized analysis set will use the following rules:

- participants will be evaluated according to the study intervention they have been assigned to (which may be different from the study intervention they have received)
- all available data will be included (e.g., including assessment after study intervention discontinuation).

2.3.2. Full Analysis Set (FAS)

This includes all randomized participants who have received at least one dose of study intervention/medication and have at least one post-baseline KCCQ measurement.

- Randomized participants in this analysis set will be considered regardless of when they received/started their first dose of study intervention/medication.
- all available data will be included (e.g., including assessment after study intervention discontinuation).

Analyses of the primary, secondary, and exploratory endpoints in this study will be based on the full analysis set (FAS).

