4.2. Scientific Rationale for Study Design

Study Population

The study population selected represents participants with HF (HFrEF and HFpEF), with or without T2DM, who would potentially benefit from a drug intervention that could offer improvement in health status outcomes, such as clinical symptoms (eg, dyspnea and fatigue commonly experienced by these participants) and impaired quality of life (eg, physical limitations and emotional dysfunction such as depression and anxiety). Participants who meet the inclusion criteria for these conditions include adults of any gender 18 years of age and older, representing the demographic group in which these conditions are prevalent, and mortality and hospitalization rates are high, despite the recommendations of existing clinical practice guidelines.

Length of Study Periods

The screening period of 28 days allows for an appropriate length of time for screening procedures to determine study eligibility (with EHR reviews, app set-up, completion of the KCCQ, and consenting). The baseline period of 7 days begins upon randomization and allows for shipment of the study drug and Fitbit device to the participant. The 3-month, double-blind treatment period provides sufficient timepoints for effectiveness assessments to demonstrate treatment differences between canagliflozin and placebo.

Placebo Control, Randomization, Blinding, Intervention Groups

A placebo control will be used to establish the frequency and magnitude of changes in clinical endpoints that may occur in the absence of active intervention. Randomization will be used to minimize bias in the assignment of participants to intervention groups, to increase the likelihood that known and unknown participant attributes (eg, demographic and baseline characteristics) are evenly balanced across intervention groups, and to enhance the validity of statistical comparisons across intervention group. Blinded intervention will be used to reduce potential bias during data collection and evaluation of clinical endpoints.

Dose and Dosage Administration Regimen

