8.1. Effectiveness Assessments

The primary effectiveness endpoint (KCCQ TSS) will be assessed at baseline and Weeks 2, 4, 6, and 12 during the double-blind treatment period (first 3 months) and afterwards at 6 and 9 months when no study intervention is administered. The following sensor data will be obtained from the Fitbit: step count and floors climbed.

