9. STATISTICAL CONSIDERATIONS

Statistical analysis will be done by the sponsor or under the authority of the sponsor. A general description of the statistical methods to be used to analyze the effectiveness and safety data is outlined below. Specific details will be provided in the SAP.

The primary study objective will be addressed by comparing the mean change in KCCQ TSS from baseline to Month 3 between the study intervention groups. The key secondary study objective will involve a comparison between the 2 randomized groups in terms of the mean difference in daily step counts from baseline to Month 3. For analyzing the primary, secondary, and exploratory objectives, an intent-to-treat (ITT) population comprising of all randomized participants will be used. Specific imputation rules for missing data (eg, missing KCCQ TSS, daily step count) will be applied, if warranted, and will be specified in the SAP before the final database lock. Descriptive statistics such as mean, median, standard deviation, interquartile range, minimum and maximum will be used to summarize continuous variables. Counts and proportions will be used to summarize categorical variables. Graphical data displays (eg, box plots) may be employed to summarize data. For time to event variables, Kaplan-Meier estimates over time will be plotted. All statistical tests will be two-sided and performed at the 5% significance level unless otherwise specified. No multiplicity adjustment to the overall Type I error rate will be applied when analyzing the exploratory variables.

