9.4.2. Effectiveness Analyses

9.4.2.1. Primary and Secondary Effectiveness Analyses

The primary and key secondary effectiveness analyses will be based on the ITT analysis population (using all randomized participants).

As KCCQ TSS is measured repeatedly over time (ie, at baseline, Week 2, Week 4, Week 6, and Week 12 respectively), the primary effectiveness endpoint (change in KCCQ TSS from baseline to Month 3) will be analyzed by a mixed effect model repeated measures (MMRM) method simultaneously adjusting for study intervention group, stratification factor (HF_rEF versus HF_pEF), time, time by study intervention group, and baseline KCCQ TSS value as covariates. An unstructured covariance structure will be assumed across study intervention groups to model the within-participant errors. The primary comparison will be based on the difference in least squares between treatments at Month 3. The treatment difference in the least squares means and their 2-sided 95% confidence interval (CI) will be provided. An MMRM model accounts for data missing at random.

A responder analysis will also be performed when comparing proportions of participants with a 5- (or 10-) point improvement in KCCQ TSS from baseline between the study intervention groups. This will be based on a two-sample difference in proportions test along with a 95% confidence interval for the difference in 2 proportions. Additionally, empirical cumulative distribution functions of the KCCQ TSS and other domain scores will be presented.

The primary effectiveness endpoint will also be analyzed by subgroups defined by age, gender, race and key baseline disease/demographic characteristics using the MMRM approach described above. Further details will be provided in the SAP. Quantitative and/or qualitative interactions for each subgroup and treatment will be identified. Qualitative interactions will be investigated further by the Gail and Simon test⁹ and interpreted accordingly.

The first key secondary endpoint of daily step count will be tested once the primary endpoint is shown to be significant at the 5% significance level using a two-sided t-test. This approach will control for the overall Type I error rate at 5%.

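### The SAP's full analysis set requires a post-baseline KCCQ even for time to death, so that analysis is death-free through Day 10 after first dose by construction, although the protocol analyses all randomised participants

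*SAP*

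**What the plan says.** **Population.** For the full analysis set (FAS), SAP 2.3.2 sets two conditions: "This includes all randomized participants who have received at least one dose of study intervention/medication and have at least one post-baseline KCCQ measurement". The same section assigns the primary, secondary and exploratory endpoints to the FAS, and SAP Appendix 4 ticks only the FAS for exploratory endpoints. Protocol section 9 says otherwise: "For analyzing the primary, secondary, and exploratory objectives, an intent-to-treat (ITT) population comprising of all randomized participants will be used". Protocol 9.4.2.1 repeats this for the primary and key secondary analyses.

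**Endpoints.** Time to death, the two time-to-first-hospitalisation endpoints and healthcare resource use (HRU) are exploratory (SAP 5.4.1). SAP 5.4.2 gives the event endpoints a Cox model and Kaplan-Meier curves. Neither that section nor SAP section 9 names another analysis set for them.

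**Timing.** Protocol 8.1: "The primary effectiveness endpoint (KCCQ TSS) will be assessed at baseline and Weeks 2, 4, 6, and 12 during the double-blind treatment period". SAP Table 1 gives Days 11 to 17 as the Week 2 window, and SAP 2.1 adds: "Study app is programmed to allow PRO measurements to be recorded only within a pre-specified window of days around each scheduled time point". Study Day 1 is the first dose (SAP 2.5), and SAP 2.1 notes that "the first study intervention may be started by a participant a few days after the actual randomization date". Protocol 4.2 explains the gap: "The baseline period of 7 days begins upon randomization and allows for shipment of the study drug and Fitbit device to the participant".

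**The concern.** A completed questionnaire is a sensible entry condition for a questionnaire endpoint. It has no bearing on death or hospitalisation, which come from claims and death data. Requiring it means that a participant must survive long enough to be asked, and then answer, before a death can count. The mortality curve therefore opens with a stretch of guaranteed survival. Time to hospitalisation and HRU lose anyone who never completes a post-baseline KCCQ.

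The set is also defined by something that happens after randomisation, so the comparison of event times is no longer fully protected by randomisation. SAP section 2 nevertheless presents FAS analyses as following the intent-to-treat principle. The step-count estimand in SAP 5.3.2 carries the same KCCQ condition, and step count is the second test in the fixed sequence of SAP 1.3.

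**Working it through.** **1. The window.** Week 2 is Day 14 with 3 days either side: 14 − 3 = 11 and 14 + 3 = 17, which reproduces the 11 to 17 of SAP Table 1. The same rule reproduces the windows for Week 4 (25 to 31), Week 6 (39 to 45) and Week 12 (81 to 87). The last day on which no post-baseline KCCQ can exist is 11 − 1 = Day 10.

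**2. Guaranteed death-free time, counted from first dose.** Treatment period: 10/84 = 11.9%. Whole study: 10/252 = 4.0%. This follows from the rules and needs no mortality assumption. It is a minimum, because a later death with no completed KCCQ is excluded as well.

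**3. Counted from randomisation.** The actual gap to first dose is not given. If it were the full 7 days of the baseline period, the death-free time would be (10 + 7)/(84 + 7) = 17/91 = 18.7% up to Day 84, and 17/259 = 6.6% over the study. The added 7 days also fail the dose condition, so they cannot be put down to the KCCQ condition alone.

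**4. Post-dose deaths lost.** The documents give no expected mortality, so 12-week mortality m is assumed, with a constant hazard L = −ln(1 − m)/84. The probability of dying on Days 1 to 10 is 1 − exp(−10L). N = 400 to 480 is the enrolment anticipated in SAP 1.4. The last column is 1 − exp(−74L), assuming that everyone alive after Day 10 completes a KCCQ.

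| m (assumed) | P(death, Days 1–10) | Deaths lost, N = 400–480 | 12-week mortality shown in FAS |
|---|---|---|---|
| 1% | 0.00120 | 0.5–0.6 | 0.88% |
| 2% | 0.00240 | 1.0–1.2 | 1.76% |
| 5% | 0.00609 | 2.4–2.9 | 4.42% |

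About 12% of 12-week post-dose deaths are lost in each row. The 5% row is the level in SAP 5.2.3 above which joint modelling is considered. The SAP does not expect it.

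**5. Primary analysis.** The mixed model in SAP 5.2.3 uses change scores. A participant with no post-baseline KCCQ has none, so dropping that participant leaves the fitted data essentially the same.

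**6. Step count.** Its baseline is the average of Days 1 to 14 (SAP 2.1, 5.3.1). Anyone dead by Day 10 has no post-baseline interval under any population rule. The KCCQ condition matters here only for survivors who never complete a KCCQ. Their number is not given; each 1% is 4 to 5 people at N = 400 to 480.

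**The case against.** **Early deaths are not hidden.** Disposition covers all randomised participants, with a Kaplan-Meier curve of time to study termination (SAP 4.2, Appendix 4). Deaths after dosing can appear in the safety set and in the listing of treatment-emergent deaths (SAP 6.1). This stands as mitigation, but none of these outputs corrects the time-to-death curve or its Cox estimate.

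**The numbers are small and the endpoint is exploratory.** SAP 5.2.3 expects low mortality, and entry criteria select clinically stable patients and exclude recent decompensation and short life expectancy. A constant hazard from Day 1 may therefore overstate early deaths. At 440 participants and 2% mortality there are about 8.8 deaths, and the 95% limits of the hazard ratio lie a factor of exp(1.96 × 2/√8.8) ≈ 3.75 either side. Losing 12% of deaths makes that about 4.1. Under proportional hazards, starting both arms at Day 11 does not shift the hazard ratio. All of this stands and limits the severity.

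**Few survivors may be lost.** Any one of six post-baseline KCCQs qualifies (Weeks 2, 4, 6 and 12, Months 6 and 9), with app reminders and payment on completion. This is plausible, but the documents do not size it.

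**The switch was deliberate.** The SAP's summary of changes records the move to the FAS. It gives no reason for applying a KCCQ condition to endpoints that need none, and the current protocol still names all randomised participants.

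**Stronger readings.** A reader might infer that the KCCQ condition causes every loss from randomisation to Day 10. It does not: deaths before first dose fail the dose condition whatever the KCCQ rule. A reader might also infer that a firm rule scoring deaths as the worst response is defeated. SAP 5.2.3 makes that handling optional in the responder analysis and only a possibility for the win ratio. Finally, a reader might infer that early deaths distort the step-count test; step 6 of the working shows that they cannot.

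**Conclusion.** The point holds. As written, the time-to-death analysis excludes every death through Day 10 after first dose, 11.9% of the treatment period, in conflict with protocol section 9. Deaths between randomisation and first dose are excluded too, by the dose condition as well. Time to hospitalisation and HRU lose anyone who never completes a post-baseline KCCQ.

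The expected loss is about 0.5 to 1.2 post-dose deaths at 400 to 480 participants, on the assumptions of a constant hazard and 12-week mortality of 1% to 2%. It would be 2.4 to 2.9 at 5%. Absolute early mortality is understated. The documents do not support a claim that the hazard ratio is biased in a given direction: that would need early death or KCCQ non-completion to differ by arm. Nor is the primary result at risk. The change is still worth making, because these endpoints do not depend on a questionnaire and a suitable set is already defined.

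**What to change.** 1. Analyse time to death, both time-to-hospitalisation endpoints and HRU in the all randomized analysis set (SAP 2.3.1). Count event times from randomisation; the SAP states no time origin for time to death. Amend SAP 2.3.2, 5.4.2 and Appendix 4 to match.
2. If deaths are counted in the optional responder or win-ratio analyses, use all dosed participants (the safety set, by randomised arm) so that early post-dose deaths are included, and state a rule for survivors with no Week 12 score. All randomised participants would not work here, because a never-dosed participant has no Study Day 1 and so no Week 12.
3. Remove the KCCQ condition from the step-count estimand in SAP 5.3.2, so that dosed participants with valid baseline and post-baseline Fitbit intervals contribute. This recovers no early deaths, and its effect cannot be sized from the documents.
4. Leave the primary mixed model as it is and reconcile the population wording in protocol 9 and 9.4.2.1, SAP 2.3.2 and Appendix 4. Include the subgroup text in SAP 5.2.3, which names the all randomized set where Appendix 4 ticks only the FAS and per protocol set for the primary endpoint.

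The cost is wording and one missing-score rule, with no new data collection. SAP 1.6 already pulls claims for randomised participants, and protocol 7.2 already seeks vital status after loss to follow-up. The downsides are slight dilution from never-dosed participants in the event analyses and incomplete capture for some: claims depend on a successful match (SAP Appendix 5), and vital status is attempted, not assured.
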